5.1.2 Exclusion Criteria

1. Subject has spontaneously improving or rapidly deteriorating plaque psoriasis.
2. Subject has guttate, pustular, erythrodermic or other non-plaque forms of psoriasis.
3. Subject has a physical condition which, in the investigator's opinion, might impair evaluation of plaque psoriasis, adrenal axis function (e.g., Addison's Disease, Cushing's Syndrome) or which exposes the subject to an unacceptable risk by study participation.
4. Subject has used any phototherapy (including laser), photo-chemotherapy or systemic psoriasis therapy including methotrexate, retinoids, cyclosporine or biologics within 30 days prior to the initiation of treatment with the test article.
5. Subject has used systemic corticosteroids (including oral or intramuscular) or topical, inhaled or intranasal corticosteroids within 30 or 14 days, respectively, prior to Part B of the Screening Visit and/or the subject has used systemic or topical corticosteroids between Part B of the Screening Visit and the initiation of treatment.
6. Subject has had prolonged exposure to natural or artificial sources of ultraviolet radiation within 30 days prior to the initiation of treatment or is intending to have such

⁶ Effective forms of birth control include hormonal contraceptives [oral, injectable, transdermal or intravaginal] or intrauterine device (IUD) for two cycles (e.g., eight weeks) prior to test article application, condom and spermicidal or diaphragm and spermicidal). Other acceptable forms of birth control include: a) abstinence for subjects who are not sexually active or b) if the subject is in a monogamous relationship with a partner who is sterile (e.g., vasectomy performed at least six months prior to the subject's initiation of treatment). Subjects who become sexually active or begin to have relations with a partner who is not sterile during the trial must agree to use an effective form of birth control for the duration of the study.

exposure during the study that is thought by the investigator to likely modify the subject's disease.

7. Subject has used topical psoriatic therapy including tar, anthralin, retinoids, vitamin D analogs (e.g., Dovonex[®]) within 14 days prior to the initiation of treatment with the test article.
8. Subject has used emollients/moisturizers on areas to be treated within one day prior to the initiation of treatment with the test article.
9. Subject is currently using lithium or Plaquenil (hydroxychloroquine).

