8. PRIOR AND CONCOMITANT THERAPIES

Current medications and any medications taken in the 45 days prior to Visit 1 (Screening) will be recorded as prior/concomitant medications with the corresponding indication. The medications to be recorded include prescription and over-the-counter medications (except vitamins and dietary supplements). All medications taken on a regular basis should be recorded on the CRFs prior to commencing the use of the test article.

Therapies (medication and non-medication therapies) not restricted by the protocol may be used during the study for the treatment or prevention of disease or to maintain good health. Vitamins and mineral supplements are permitted at dosages considered by the investigator

as reasonable for maintaining good health. Non-prohibited chronic therapies being used at Visit 1 may be continued. Any changes in concomitant therapies during the study must be recorded on the CRFs. The reason for any change in concomitant medications or therapies/procedures should be reported and should reflect either a baseline medical condition documented in the medical history of the CRF or an AE.

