10.1 Visit 1 – Screening Visit (-Day 20 or Longer)

This visit should be scheduled between 7 and 8AM given the timing requirements for the study and the CST should be performed a minimum of 20 days before the Baseline Visit.

PART A

At this visit, the investigator or designee will:

- Obtain a signed, written informed assent from the subject. The subject must be accompanied by the parent or legal guardian at the time of assent/consent signing. The parent or legal guardian must provide informed consent for the subject. Consent/assent must be signed prior to the initiation of any study-related procedures.
- Assign each eligible subject a “screening” number.
- Complete the Medical History and Demographics Form.
- Review current medications and therapies.
- Confirm the subject meets the inclusion/exclusion criteria.
- Have the subject complete washout from any prohibited medications, if necessary. This may require that the subject return to the clinic to complete the remaining visit procedures.
- Schedule the Visit for Part B; ideally at least 20 days prior to the Baseline (Day 1) Visit.

PART B

NOTE: Part B activities can be done concurrently with Part A if no washout period is required but should occur a minimum of 20 days prior to the Baseline (Day 1) Visit.

At this visit, the investigator or designee will:

- Perform a UPT for all female subjects; the results must be negative for the subject to participate in Part B of the screening phase.
- Record changes to current concomitant medications and therapies.
- Reconfirm the subject meets the inclusion/exclusion criteria.
- Record vital signs, height and weight.
- Record IGA score.
- Perform a CST, see [Section 13.1](#). CST should be initiated between 7 and 9AM at this visit. If the CST cannot be initiated before 9AM, another visit should be scheduled to complete Part B.

- Draw blood for Baseline drug concentration in plasma.
- Inform the subject that if the serum cortisol levels or CST results are not within the normal range, he/she will not be eligible for the study.
- Schedule Visit 2 (Day 1/Baseline Visit). This visit should ideally be scheduled at least 20 days after completion of Visit 1, Part B.
- Update the Subject Screening and Enrollment Log.

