14.3 Screen Failures

If a subject is a screen failure due to Visit 1 laboratory results that show an abnormal pre-CST serum cortisol level or abnormal HPA axis function (a low post-CST serum cortisol level), complete the Screen Failure CRF. No clinical evaluation or follow-up CST will be performed in these subjects; however, the laboratory results will be provided to the subject's parent with a recommendation to follow up with the subject's regular healthcare provider.

If a subject withdraws prematurely during the treatment period for another reason, complete the CRF for the appropriate visit, then complete the End of Study CRFs including scheduling appropriately to obtain the End of Study CST assessment.

Subject enrollment will continue until at least 20 subjects with both Screening and End of Study serum cortisol data (pre- and post-cosyntropin stimulation) have completed the study without any significant protocol violations (evaluable subjects). This may require the enrollment of approximately 25 subjects.

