The usual normal response in most cases is an approximate doubling of the basal level, provided that the basal level does not exceed the normal range. Patients receiving cortisone, hydrocortisone or spironolactone should omit their pre-test doses on the day selected for testing. Patients taking inadvertent doses of cortisone or hydrocortisone on the test day and patients taking spironolactone or women taking drugs which contain estrogen may exhibit abnormally high basal plasma cortisol levels. A paradoxical response may be noted in the cortisone or hydrocortisone group as seen in a decrease in plasma cortisol values following a stimulating dose of CORTROSYN®.

In the spironolactone or estrogen group only a normal incremental response is to be expected. Many patients with normal adrenal function, however, do not respond to the expected degree so that the following criteria have been established to denote a normal response:

1. The control plasma cortisol level should exceed 5 micrograms/100 mL.
2. The 30-minute level should show an increment of at least 7 micrograms/100 mL above the basal level.
3. The 30-minute level should exceed 18 micrograms/100 mL. Comparable figures have been reported by Greig and co-workers (2).

Plasma cortisol levels usually peak about 45 to 60 minutes after an injection of CORTROSYN® and some prefer the 60-minute interval for testing for this reason. While it is true that the 60-minute values are usually higher than the 30-minute values, the difference may not be significant enough in most cases to outweigh the disadvantage of a longer testing period. If the 60-minute test period is used, the criterion for a normal response is an approximate doubling of the basal plasma cortisol value.

In patients with a raised plasma bilirubin or in patients where the plasma contains free hemoglobin, falsely high fluorescence measurements will result. The test may be performed at any time during the day but because of the physiological diurnal variation of plasma cortisol the criteria listed by Wood cannot apply. It has been shown that basal plasma cortisol levels and the post CORTROSYN® increment exhibit diurnal changes. However, the 30-minute plasma cortisol level remains unchanged throughout the day so that only this single criterion should be used (3).

Parenteral drug products should be inspected visually for particulate matter and discoloration whenever solution and container permit. Reconstituted CORTROSYN® should not be retained.

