#### 8.2.2 *Evaluable Population*

The Evaluable population will include those subjects in the Safety population who have both Screening and EOS serum cortisol data (pre- and post-cosyntropin stimulation) and meet the following criteria:

- Meets all inclusion/exclusion criteria, including normal response to cosyntropin stimulation defined as a Screening CST with a 30-minute post-stimulation cortisol level  $>18 \mu\text{g/dL}$ .
- Screening and EOS CST were conducted between 7-9 AM.
- EOS CST was conducted within  $\pm 1$  hour of the Screening CST.
- Applied at least 80% and no more than 120% of the expected number of applications and applied the final dose no more than 14 hours prior to the start of the CST test.

- Has not taken or applied any medications that may interfere with HPA axis function.
- Do not have any other significant protocol deviations.

HPA axis suppression analysis will be conducted on the Evaluable and Safety populations.

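### Does the Evaluable population's medication rule need to say whether users of permitted estrogen-containing contraceptives are excluded?

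*SAP*

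**What the plan says.** SAP 8.2.2 builds the Evaluable population from Safety subjects with cortisol data at both Screening and end of study (EOS), then adds criteria. One is that the subject "Has not taken or applied any medications that may interfere with HPA axis function". There is no drug list, no time window and no named adjudicator. The criterion after it rules out any *other* significant deviations.

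Female subjects must agree to effective birth control (Protocol 5.1.1, criterion 6). The footnote on this begins "Effective forms of birth control include hormonal contraceptives [oral, injectable, transdermal or intravaginal" and also accepts barrier methods, abstinence and "intrauterine device (IUD) for two cycles (e.g., eight weeks) prior to test article application". Protocol 8.1 prohibits psoriasis treatments and steroids, giving hydrocortisone products as an example, and does not mention estrogen. Protocol 8 adds: "Therapies (medication and non-medication therapies) not restricted by the protocol may be used during the study for the treatment or prevention of disease".

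The cosyntropin insert in Protocol Appendix 4 says that "women taking drugs which contain estrogen may exhibit abnormally high basal plasma cortisol levels", and then: "In the spironolactone or estrogen group only a normal incremental response is to be expected".

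At Screening, subjects are told that "if the serum cortisol levels or CST results are not within the normal range, he/she will not be eligible for the study" (Protocol 10.1). Protocol 14.3 counts as screen failures those with "Visit 1 laboratory results that show an abnormal pre-CST serum cortisol level".

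The endpoint is a 30-minute post-stimulation cortisol of 18 µg/dL or less (Protocol 18.2.2). SAP 8.9.3 reports the suppressed proportion with a 95% confidence interval in both the Evaluable and the Safety populations.

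**The concern.** The rule covers any medication that might interfere and is not limited to prohibited ones. The protocol's own appendix names estrogen as a drug that alters measured cortisol, and SAP 9 says the Evaluable criteria exist to make the stimulation tests comparable between subjects. Taken together, these could lead an analyst to exclude a girl on a combined contraceptive. A colleague could keep her because the product is permitted. The two would then report different denominators, and possibly different numerators, for the HPA suppression proportion in the population that SAP 9 assigns to it.

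The protocol's count toward 20 evaluable subjects (18.1) contains no medication rule. A user could therefore count toward the recruitment target and later drop out of the analysis set. With about 20 subjects, each one is 1/20 = 5% of the denominator.

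**Working it through.** **Which reading fits the text?**

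- *For exclusion:* the breadth of the rule, the insert's remark on basal cortisol, and the comparability aim in SAP 9.
- *For keeping users:* the word *other* in the next criterion marks the preceding items as deviations, and using birth control that the protocol accepts is not a deviation. The rule concerns HPA axis function, whereas the insert describes a raised basal level with a normal increment. Nothing in the documents says that estrogen impairs the axis or turns a suppressed 30-minute value into a normal one.

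The second reading is the stronger.

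**What is already covered?** A user established before Screening takes the Screening test on the product. If her basal cortisol is abnormal, Protocol 10.1 and 14.3 make her a screen failure. This cover has limits. The exclusion list in 5.1.2 names only the 30-minute value, so it depends on sites applying 10.1 and 14.3. The eight-week lead-in may attach only to the IUD. A product started after the Screening test is not seen.

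**How large could the effect be?** The plan has no power calculation to reproduce. Its figures are at least 20 evaluable from about 25 enrolled. 20/25 = 80%, so 25 is consistent with a 20% loss, but no loss rate is stated.

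Assumptions, not document figures:

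- 20 otherwise Evaluable subjects;
- 5 suppressed, close to the adult lotion rate in Protocol 1 (5/21 = 23.8%);
- *k* users removed under the exclusion reading;
- Clopper-Pearson intervals, because the SAP names no method.

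For x events in n subjects, the lower limit is the 2.5% point of Beta(x, n − x + 1) and the upper limit is the 97.5% point of Beta(x + 1, n − x).

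| Users removed | All removed users suppressed | No removed user suppressed |
|---|---|---|
| 0 | 5/20 = 25.0% (8.7 to 49.1) | 5/20 = 25.0% (8.7 to 49.1) |
| 1 | 4/19 = 21.1% (6.1 to 45.6) | 5/19 = 26.3% (9.1 to 51.2) |
| 2 | 3/18 = 16.7% (3.6 to 41.4) | 5/18 = 27.8% (9.7 to 53.5) |
| 3 | 2/17 = 11.8% (1.5 to 36.4) | 5/17 = 29.4% (10.3 to 56.0) |

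With no events, the upper limit is 1 − 0.025^(1/n): 16.8% for n = 20, 17.6% for 19, 18.5% for 18 and 19.5% for 17.

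The interval for 5/20 is 49.1 − 8.7 = 40.4 percentage points wide. One user moves the estimate by −3.9 or +1.3 points. Even the extreme case of three users, all suppressed, gives 11.8%, inside 8.7 to 49.1. That case is also implausible on the insert's account: a raised basal level with a normal increment makes a value of 18 or below less likely.

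**The case for a change.** The strongest case for a change concerns timing. The study is open label, and sites review EOS cortisol and report abnormal results as adverse events while the study runs. If membership is left to judgement, it may be settled when each subject's result is known. The endpoint is also an absolute cortisol level, so a drug that raises measured cortisol is not obviously irrelevant, and a product started between Screening and EOS escapes the Screening check. One sentence in the SAP would settle the matter.

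What stands is that the rule is unspecific, and that an analyst should classify such a subject from the concomitant-medication records without looking at her EOS cortisol. That is ordinary practice and needs no amendment. The planned listings of medications (SAP 8.9.7) and population membership (SAP 8.5) would let a reader see how she was handled.

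What does not stand is the case for an exclusion sentence. It would penalise use of contraception that the protocol accepts, could take the set below 20, and would drop any suppressed user from the Evaluable numerator of a safety endpoint. It would still leave the rule without a drug list or time window for everything else, including spironolactone, which the insert names alongside estrogen. The mismatch with Protocol 18.1 is not specific to estrogen either: the SAP's 14-hour limit on the final dose is also absent there.

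**Conclusion.** No change is needed. This is a gap in detail that analysts can fill sensibly, and the text favours keeping permitted users in the Evaluable population. Either reading gives a sound descriptive estimate, and the Safety estimate is the same under both.

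On the assumed 5 suppressed of 20, one user of open status moves the Evaluable proportion from 25.0% to 21.1% or 26.3%, well within sampling uncertainty. With no users, nothing moves. Zero is possible: subjects are aged 12 to 16 years 11 months, abstinence is accepted, and not every hormonal product need contain estrogen.

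The conclusion rests on three things: few users, sites applying the pre-stimulation cortisol check at Screening, and the documents' silence on any effect of estrogen on a suppressed 30-minute value. No hypothesis test or decision threshold depends on the result.

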### **8.2.3 *Pharmacokinetic Population***

Subjects included in the PK analysis (PK population) will include those subjects in the Safety population who do not have any significant protocol deviations and must have at least an 80% - 120% dose compliance based on number of applications.

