## **4. STUDY DESIGN**

This is an open label, multicenter study of an investigational formulation of HBP Lotion, 0.05% in male and female subjects aged 12 to 16 years 11 months with stable plaque psoriasis. Approximately 25 subjects with stable plaque psoriasis on at least 10% of their BSA (excluding the face, scalp, groin, axillae and other intertriginous areas), who fulfill the inclusion/exclusion criteria will be enrolled at multiple study sites. All subjects will have a screening cosyntropin stimulation test (CST) to assess their HPA axis response at Visit 1 (Screening Visit). At Visit 2 (Baseline), eligible subjects with normal adrenal function will be eligible to participate in the study.

Subjects will apply HBP Lotion, 0.05% to all psoriasis plaques identified at Visit 2 twice daily (approximately every 12 hours) for the assigned treatment period or until the investigator verifies the subject's psoriasis has cleared. All subjects will have a CST to reassess their HPA axis response at EOS (or earlier if the investigator verifies the subject's psoriasis has cleared).

Eligible subjects will have blood drawn at Screening for baseline drug concentration in plasma. On Day 8, all subjects, regardless of lesion clearance, will have blood drawn for assessment of trough drug concentration in plasma. At the Day 15 visit, subjects who have continued to treat lesions will have a final PK blood sample collected approximately 12 hours after their Day 14 evening application and just prior to the initiation of the CST.

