## **7.2 Pharmacokinetic Tests**

Blood for PK analysis will be drawn three times: at Screening (pre-application, time=0), Day 8, and Day 15 (unless IGA=0 at Day 8), approximately 12 hours after the dose on the previous day. All eligible subjects will have blood drawn at Screening for baseline drug concentration in plasma. On Day 8, all subjects, regardless of lesion clearance, will have blood drawn for assessment of trough drug concentration in plasma. At the Day 15 visit, subjects who have continued to treat lesions will have a final PK blood sample collected approximately 12 hours after their Day 14 evening application and just prior to the initiation of the CST.

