## **8.7 Dosing Compliance**

Descriptive statistics will be used to summarize test article compliance for the Evaluable and PK populations. Measures of test article compliance will include the duration of treatment (number of days dosed = last dose date - first dose date + 1), the total number of applications (determined from the actual number of applications reported by the subject), and the percent of expected doses applied. The expected number of doses for subjects who are clear at Day 8 and discontinue from the study is 14. Subjects who continue to Day 15 or early term will have the compliance rate based on an expected 28 doses. A subject will be considered compliant with the dosing regimen if the subject applies at least 80% but no more than 120% of the expected number of applications.

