#### ***8.9.4 Pharmacokinetic Analyses***

Morning trough concentrations of HBP in plasma at Screening, Day 8 and Day 15 will be summarized for the PK population using geometric mean, coefficient of variation in addition to n, mean, median, standard deviation, minimum and maximum.

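### One whole-study compliance rule selects both PK rows, so doses applied after the Day 8 draw help decide whether the Day 8 trough counts

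*SAP*

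**What the plan says.** SAP 8.2.3 admits to the PK population those members of the Safety population "who do not have any significant protocol deviations" and who "must have at least an 80% - 120% dose compliance based on number of applications". Both conditions apply to the subject, and neither is tied to a visit or a sample. Protocol 18.3 has the same rule.

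SAP 8.2.3 does not say how compliance is calculated. The only definition is in SAP 8.7, which also reports compliance for the PK population by name. It has two denominators:

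- Day 8 exits: "The expected number of doses for subjects who are clear at Day 8 and discontinue from the study is 14".
- Everyone else: "Subjects who continue to Day 15 or early term will have the compliance rate based on an expected 28 doses".

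The limits are "at least 80% but no more than 120% of the expected number of applications".

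SAP 7.2 plans the Day 8 sample for everyone: "On Day 8, all subjects, regardless of lesion clearance, will have blood drawn for assessment of trough drug concentration in plasma". SAP 8.9.4 then uses one set for every row: "Morning trough concentrations of HBP in plasma at Screening, Day 8 and Day 15 will be summarized for the PK population".

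For PK, neither document sets a compliance condition up to the Day 8 draw, a sample-level exclusion, or a limit on the interval from last dose to draw. The 14-hour limit in SAP 8.2.2 belongs to the Evaluable population and concerns the cosyntropin test only.

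**The concern.** A trough drawn on the morning of Day 8 cannot be influenced by doses applied after it. Yet for a subject who goes on to Day 15, half of the 28 doses that settle membership fall after that draw. The rule can therefore misclassify in two directions. It can discard a Day 8 value that followed a fully dosed week, and it can retain one that followed a poorly dosed week.

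The PK properties of the lotion are part of the study's stated objective, and Day 8 is the on-treatment sample planned for all subjects. If the Day 8 row is selected partly on later behaviour, it does not describe trough levels in subjects who had dosed adequately up to that point.

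**Working it through.** **Inputs.** Dosing is "twice daily (approximately every 12 hours) for the assigned treatment period" (SAP section 4), so two per day. The limits are 80% and 120%, and the denominators are 14 and 28 (SAP 8.7).

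**Reproducing the plan's denominators.** Doses due by the evening of Day 7: 2 × 7 = 14. Doses due by the evening of Day 14: 2 × 14 = 28. Both agree with SAP 8.7.

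**Limits in whole applications.**

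- Of 14: 0.80 × 14 = 11.2 and 1.20 × 14 = 16.8, so 12 to 16.
- Of 28: 0.80 × 28 = 22.4 and 1.20 × 28 = 33.6, so 23 to 33. Hence 22/28 = 78.6% fails and 23/28 = 82.1% passes.

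**Cases, for visits exactly on Day 8 and Day 15.** The last column looks at the compliance condition alone.

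| Before Day 8 draw | After | Total of 28 | Adequate up to draw? | Day 8 trough under the plan |
|---|---|---|---|---|
| 14/14 (100%) | 9/14 | 23 (82.1%) | yes | kept |
| 14/14 (100%) | 8/14 | 22 (78.6%) | yes | dropped |
| 12/14 (85.7%) | 10/14 | 22 (78.6%) | yes | dropped |
| 9/14 (64.3%) | 14/14 | 23 (82.1%) | no | kept |
| 8/14 (57.1%) | 14/14 | 22 (78.6%) | no | dropped |

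The first two rows have identical dosing up to the draw. One second-week application decides whether the Day 8 value is used.

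**How far the rule reaches.** With 0 to 14 applications in each week there are 15 × 15 = 225 possible pairs.

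- Adequate up to the draw but dropped: 12 then 0–10 (11 pairs), 13 then 0–9 (10), 14 then 0–8 (9), which is 30 pairs.
- Under-dosed up to the draw but kept: 9 then 14 (1 pair), 10 then 13–14 (2), 11 then 12–14 (3), which is 6 pairs.

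These count possibilities, not probabilities. Without extra applications, 8/14 or fewer in the first week always fails.

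**Why a kept sample can matter.** If the five doses missed in the 9/14 case were the last five before the draw, the latest application was the ninth, on the morning of Day 5. The sample would then be about 72 hours after dosing, although it is reported as a trough at about 12 hours.

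**Illustration only.** The documents give no adherence rate. Assume each dose is applied independently with probability p, and let f(x) = C(14,x) pˣ(1−p)¹⁴⁻ˣ. The share dropped although adequate is the sum of f(i)f(j) over i ≥ 12 and i + j ≤ 22. The share kept although under-dosed is the sum over i ≤ 11 and i + j ≥ 23.

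| p | Adequate but dropped | Under-dosed but kept |
|---|---|---|
| 0.80 | 9.7% | 15.0% |
| 0.85 | 5.6% | 17.2% |
| 0.90 | 1.5% | 11.8% |
| 0.95 | 0.1% | 2.8% |

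Real missed doses are unlikely to be independent, so this shows only that the issue shrinks as adherence approaches complete.

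**The case against.** The strongest reply is that a single set of subjects who followed the regimen is a conventional choice. It keeps the same subjects in both rows, and the SAP never claims that the Day 8 row describes compliance up to the draw. The PK analysis is descriptive, with no test or margin, and SAP 8.1 says that summary tables will generally be supported by listings, so individual values should remain visible. All of this stands, and it limits the seriousness of the point. It does not give a reason for using doses applied after a sample to judge that sample.

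The second reply is that the deviation condition may remove a subject who missed five of fourteen first-week doses. It may. But the term is undefined, and no text says that such missed doses qualify. Protocol 18.3 asks sites to try to prevent consecutive missed doses, which is advice and not an exclusion. Nor can this condition restore a Day 8 value that the compliance condition has dropped.

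A reader might also infer more than the documents support:

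- *That under-dosed Day 8 samples stay in as a matter of course.* They can stay, but only with 9, 10 or 11 of 14 and a near-complete second week, and only if the deviation condition does not intervene.
- *That over-dosed Day 8 samples are a comparable problem.* The sum works (19 + 14 = 33/28 = 117.9%), but it needs five extra applications in seven days and then exact dosing. That is too strained to carry weight.
- *That each misclassified subject is about 5% of the row.* The figure of 20 in protocol 18.1 is the target for evaluable cortisol data, not a PK sample size.
- *That the Day 8 estimate is biased by a known amount.* Dropping well-dosed samples biases the row only if second-week adherence is related to Day 8 concentration, and nothing in the documents shows that.
- *That the SAP departs from the protocol.* Both contain the same rule, so this is a shared weakness and not an inconsistency.

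**Conclusion.** The point holds for subjects who continue past Day 8 or terminate early. It does not apply to those who clear and exit on Day 8, whose 14-dose denominator already ends at the draw. For the affected subjects, compliance after the draw can drop a fully dosed Day 8 trough and can retain one taken after as little as 64.3% of first-week doses.

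This rests on reading SAP 8.7 as the compliance definition behind SAP 8.2.3. There is no explicit cross-reference, but no other definition exists. An early terminator who had dosed fully up to Day 8 is also lost (14/28 = 50%), but that follows mainly from applying 28 expected doses to early termination, which is a separate matter.

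The effect on the Day 8 mean or spread cannot be computed, because the documents give no concentrations, half-life or adherence rate. The analysis is descriptive and no hypothesis test is affected. The rule should be corrected because the PK profile is a stated objective and the correction is cheap, but it does not threaten the study's main conclusion on adrenal suppression.

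**What to change.** Reword SAP 8.2.3 so that inclusion is decided for each sample:

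- **Day 8 concentration:** enters if the subject applied 80–120% of the applications expected from first dose up to that draw (14 for a visit exactly on Day 8, so 12 to 16) and had no significant protocol deviation affecting dosing or sampling up to that draw.
- **Day 15 concentration:** enters on whole-period compliance and deviations.

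Tying the deviation condition to the draw is necessary. Otherwise poor second-week dosing could still remove the Day 8 value by that route.

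A cumulative count does not show whether the last doses before a draw were applied: 12/14 with the final two missed would still pass. List each sample's interval from last dose to draw, where recorded.

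The derived variable can come from the missed-dose records. Protocol Appendix 3 (A 3.6) has missed applications recorded on the compliance form and application times in the diary. Protocol 10.3 mentions dates of missed doses on the form explicitly only for subjects who have cleared, so confirm that these dates are in the database for continuing subjects too.

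Record the change in SAP section 9, which already documents changes to the protocol's populations, and do so before database lock.

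The cost is SAP wording and one derived variable. The downside is that n may differ between the Day 8 and Day 15 rows. If a within-subject comparison is wanted, also show the subjects common to both.
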